Effect of Semi-occluded Vocal Tract Therapy on the Phonation of Children With Vocal Fold Nodules

NCT05878197

22/05/2024

Study protocol

This study was approved by the Ethics Committee of Ghent University Hospital (registration number: B670201936069) and has been registered on ClinicalTrials.gov. The consolidated standards of reporting trials (CONSORT) non-pharmacologic treatment interventions (NPT) checklist were used to report the trial specifications (Boutron et al., 2017). Written informed consent was obtained from a parent of each participant.

Participants

Children between six and 12 years old (primary school) with VFNs were eligible to participate in this study. Participants were recruited between October 2019 and January 2023 during their consultations at the voice unit of Ghent University Hospital, through flyers in other hospital departments, through social media, or by referral from voice therapists who were informed about this project. All participants were diagnosed with VFNs by an otorhinolarygologist with extensive experience in voice diagnostics ([name]). This age group was chosen because these children can cooperate with voice therapy and tolerate videolaryngostroboscopy. Exclusion criteria were a history of phonosurgery, nasal or ear diseases, neurological disorders, and parent-reported pubertal voice changes.

Design

A randomized controlled study design was used. Participants were assigned to one of the three study arms (experimental group "SP", experimental group "RVT", or the control group (CG) receiving indirect treatment), depending on their time of registration. The order in which the different voice treatments were organized was determined using a random number list. No changes in the methodology were made after trial commencement.

Voice therapy

In each study arm, a short-term, intensive, group therapy program was provided. All participants received 11 hours of voice therapy spread over four consecutive days (three hours on day 1-3 and two hours on day 4). Each group consisted of a minimum of two and a maximum of five children and was guided by one experienced voice therapist ([name] or [name]). All therapy sessions were provided at Ghent University Hospital. During the study period, participants were not allowed to attend external voice therapy.

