The statistical analysis was performed using IBM SPSS Statistics 28 software (SPSS, Inc. Chicago, IL). The significance level was set at $\alpha = 0.05$. One-way ANOVAs were used to check for statistically significant differences in continuous parameters (e.g., age) between the three study arms. Fisher's exact tests were used for the comparison of categorical parameters (e.g., sex) between the three study arms. Pairwise comparisons with Bonferroni corrections ($\alpha < 0.016$) were performed when a significant difference was found between the groups. The inter- and intra-rater reliability of the CAPE-V overall severity has been examined with two-way mixed ICCs and their 95% confidence intervals, type consistency, single-rating, and interpreted following the classification of Koo and Li (2016) ((ICC > 0.9 'excellent'; $0.9 \ge ICC > 0.75$ 'good'; $0.75 \ge ICC > 0.5$ 'moderate'; ICC ≤ 0.5 'poor'). The effects of voice therapy were evaluated using two complementary approaches.

Firstly, a more traditional group-level analysis was conducted. Linear mixed models were used to compare groups over time on the primary outcome parameters, using the restricted maximum likelihood estimation and unstructured covariance type. Time, group, and time-by-group interaction were specified as fixed factors. A random intercept for participants was included and within-group effects of time were determined using pairwise comparisons. Unstandardized effect sizes were presented in the form of the estimated mean differences and 95% confidence intervals for the outcome variables. For the analysis of the AVQI, only participants in whom the SNR of the pretest and posttest voice samples was greater than or equal to 30 dB were selected (Deliyski et al., 2006).

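### The group-level plan fits a time-by-group interaction but names only within-group pre/post follow-up, so the differences in change between each technique and control are not committed to

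*Combined protocol and SAP*

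**What the plan says.** All of the relevant analysis text is in the Statistical analysis plan.

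- **Purpose of the model:** "Linear mixed models were used to compare groups over time on the primary outcome parameters".
- **Fixed effects:** "Time, group, and time-by-group interaction were specified as fixed factors".
- **Named follow-up of the model:** "within-group effects of time were determined using pairwise comparisons".
- **Effect measure:** "Unstandardized effect sizes were presented in the form of the estimated mean differences and 95% confidence intervals for the outcome variables". The sentence does not say which difference is meant. It could be the change within an arm, the difference between arms at posttest, or the difference between arms in change.
- **Bonferroni comparisons:** pairwise comparisons "were performed when a significant difference was found between the groups". This sentence follows the ANOVA and Fisher tests of arm characteristics (the examples are age and sex). It comes before the sentence that opens the treatment-effect analysis.

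The control is not untreated. The Design section describes "the control group (CG) receiving indirect treatment", and the Voice therapy section says "All participants received 11 hours of voice therapy spread over four consecutive days". The individual-level analysis gives percentages with Wilson intervals and states no comparison between arms. No section names SP-CG, RVT-CG or SP-RVT differences in change.

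**The concern.** The experimental arms share counselling and breathing work with CG and add a direct technique. The natural question is therefore whether adding SP or RVT changes outcomes more than CG does. The quantities that answer it are the SP-CG and RVT-CG differences in change.

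Followed as written, the plan yields two things: a 2-df test that says the arms differ somewhere, and pre/post results within each arm. The first does not locate the difference. The second does not compare arms: one arm can reach significance while another with the same true change does not. Because CG is also treated, some pre/post change is plausible in every arm, so this matters in practice. A reader who uses the arm-specific results to locate the effect may credit a technique that does no better than control.

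**Working it through.** The plan states no sample size, SD of change, effect size or power, so it has no figure of its own to reproduce. From the documents come three arms, two assessment times and alpha = 0.05. Everything else below is assumed.

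**1. The interaction cannot locate the effect (exact, given assumed n and d).** With three arms and two times it has 3 - 1 = 2 numerator df. Take n children per arm, change scores with SD 1, and observed mean changes relative to CG, in the order SP, RVT, CG, of (d, 0, 0), (0, d, 0) or (d, d, 0). The between-arm sum of squares is n × (2/3) × d² in all three patterns. With n = 15 and d = 1 it is 15 × 2/3 = 10. Then F = (10/2)/1 = 5.0 on 2 and 3 × 14 = 42 df, and p = (1 + 2 × 5/42)^(-21) = 0.011. The result is the same whether SP alone, RVT alone or both exceed CG.

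**2. Within-arm tests as a guide to location (simulation).** Change scores have SD 1, with pooled residual variance on 3(n - 1) df, two-sided 5% tests, and n = 8, 10, 15, 20 per arm. RVT and CG share a common change b. SP has b + e, with e = 0.8 or 1.0. SP is thus the only arm that truly differs from CG.

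| Quantity | b = 0.3-0.7 |
|---|---|
| Interaction significant, all trials | 32-90% |
| RVT significant within-arm and CG not, given a significant interaction | 10-28% |
| Same pattern with a significant interaction, all trials | 3-23% |
| Mirror pattern (CG significant, RVT not), given a significant interaction | 10-28% |
| Direct RVT-CG contrast wrongly favours RVT, unadjusted, given a significant interaction | 3-7% |
| Same contrast, Bonferroni | 1-3% |

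The 10-28% depends on the assumed common change. At b = 0 or b = 1.0 it is about 1-25%.

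**3. Precision of the direct contrast.** With equal arms, the standard error of a difference in change is √2 = 1.41 times that of a change within one arm. At n = 15 the half-widths, in SD of change, are:

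- within-arm: 2.018/√15 = 0.52
- between-arm: 2.018 × √(2/15) = 0.74
- between-arm with Bonferroni for three contrasts: 2.494 × √(2/15) = 0.91, which is 0.91/0.52 = 1.75 times the within-arm half-width

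**The case against.** The strongest reply is that this is a gap in presentation, not a missing comparison. The model is declared as a comparison of groups over time and contains the interaction. If the mean differences are within-arm, the arms are independent: SP-CG is one reported estimate minus another, and its standard error is the root of the sum of the squared standard errors. If they are between-arm, much of the problem disappears. This stands in part. The size of each difference can be derived, so it would be wrong to say that the plan leaves it unknowable. But the plan does not commit to the contrasts or to a multiplicity rule for them.

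A second reply is that the Bonferroni sentence supplies the pairwise comparisons. By position it belongs to the checks of arm characteristics. Even read more widely, it does not say that it concerns differences in change.

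A third reply is that the simulated error is a reader's misuse and not a planned step. That is fair, and it limits what can be claimed:

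- A reader might infer that the plan ranks the arms by within-arm p-values. It does not say so.
- A reader might infer that, with equal true change in all arms, a technique arm would often look better than control. That occurs in 19-38% of trials only if the interaction is ignored: (1 - p)(1 - (1 - p)²) is 0.357, 0.375 and 0.192 at within-arm power p of 0.3, 0.5 and 0.8, and simulation gives 19-37%. If the interaction is respected, it is 1.5-2.7%.
- A reader might infer a bias toward the technique arms. The mirror pattern is equally frequent, so this is noise in both directions.
- A reader might infer that RVT would be credited instead of SP. In the trials showing the pattern, SP's change exceeded RVT's in about 89-99.9%. The likely error is to credit RVT as well as SP.

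**Conclusion.** The point holds as a gap that should be fixed. The plan has a valid omnibus test between arms, but it names no arm-specific comparison with control and leaves its effect measure undefined. The documents do not support the claim that between-arm inference is absent, or that the between-arm differences could not be recovered.

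That the 2-df test cannot locate the effect is exact for equal arms. The 10-28% (about 1-25% at a common change of 0 or 1.0 SD) is an illustration. It rests on assumed arm sizes, on a true difference for SP only, and on a reader who uses within-arm significance to locate it. The fair comparison is with the unadjusted contrast at 3-7%, because the within-arm tests are unadjusted too; part of the further drop to 1-3% is due to Bonferroni.

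**What to change.** In the group-level section, after the interaction, add wording to this effect: *The mixed-model differences in change (post minus pre) SP-CG and RVT-CG, and SP-RVT if that comparison is of interest, are reported with estimates and 95% confidence intervals. Familywise error over these contrasts is controlled by [testing them only if the interaction is significant / Bonferroni]. The estimated mean differences include these contrasts. Within-group changes are supportive and are not evidence that one arm is better than another.*

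Either multiplicity rule will do; one should be named. With three arms, gating on the interaction is sufficient without Bonferroni: if all arms are equal the omnibus test holds the error at 5%, and if exactly two are equal only one true null hypothesis remains. SP-RVT is optional because the documents state no hypothesis for it.

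**Cost.** No new data or model are needed. With CG as reference, the interaction coefficients are SP-CG and RVT-CG, and their difference is SP-RVT. The price is precision: intervals are about 1.4 times as wide as within-arm ones, or about 1.75 times with Bonferroni. In the scenario above, the SP-CG contrast gated on the interaction detects the true effect in about 25-85% of trials unadjusted and 18-76% with Bonferroni (71% and 60% at 15 per arm, e = 1.0 SD), so it can miss a real difference.

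**Timing.** The Participants section says "Participants were recruited between October 2019 and January 2023", and the plan, dated 22/05/2024, is written in the past tense. Contrasts added after results were seen must be labelled post hoc.
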